11.2 Disease and Medical History

Details of History of BOS diagnosis eCRF page [FVC (absolute), FVC - % of personal best post-transplant, FEV₁ (absolute), FEV₁ - % of personal best post-transplant, **CCI** (absolute), **CCI** - % of personal best post-transplant and FEV₁/FVC (ratio)], details of Historical Spirometry eCRF page [FVC (absolute), FEV₁ (absolute), **CCI** (absolute) and FEV₁/FVC (ratio)] as well as details related to each patient's lung transplant as recorded in the Lung Transplantation History eCRF page [type of underlying indication for lung transplant, time between lung transplantation and onset of BOS, donor gender, cytomegalovirus (CMV) status donor, CMV status recipient, Epstein Barr Virus (EBV)-status donor, EBV-status recipient, receive induction therapy, receive antiviral/antifungal/antibacterial therapy, cold ischemia duration for right and left lung] will be summarized by treatment group for SAF, FAS and PPS.

Disease history, including the details from the Risk Factors eCRF will be listed by FAS.

Time (days) between lung transplantation and onset of BOS is defined as the duration between date of lung transplantation and onset of initial BOS + 1.

All other significant medical conditions (including gastro-esophageal reflux disease) and procedures (including past surgeries) occurring before the informed consent form is signed will be recorded as medical history.

Medical history will be coded using the Medical Dictionary for Regulatory Activities (MedDRA) [Version 23.1] and will be presented by Internationally Agreed order System Organ Class (SOC) and Preferred Term (PT) and total. The SOCs and PTs are to be sorted by SOC and descending PTs.

L-CsA:

Treatment of BOS after SLT

Protocol Number:

BT – L-CsA – 301 – SLT

Sponsor:

Zambon SpA

Medical history will be summarized by treatment group and overall for the SAF, FAS and PPS as follows:

- The number and percentage of patients with at least one medical history record will be presented.
- The number and percentage of patients with at least one medical history record within each primary SOC and PT will be presented. The summary will be sorted using the internationally agreed order for SOC and using descending order of overall numerical counts for PT. Where terms tie, these will be sorted alphabetically.

Medical history records will be listed by-patient and within-patient by medical history start date for the FAS.

11.3 Baseline Lung Allograft Dysfunction

Baseline Lung Allograft Dysfunction (BLAD) at time of personal best post-transplant FEV₁ (Yes, No) will be reported in the demographic table. BLAD patients are defined as patients with personal best post-transplant FEV₁/predicted FEV₁*100 <80% [7]. The following formula for the calculation of predicted FEV₁ will be used:

$$\text{Predicted FEV}_1 = b_0 + b_1 * \text{age} + b_2 * \text{age}^2 + b_3 * \text{height}^2$$

where the coefficients of the regression are reported in Table 2.

Table 2: Coefficients for FEV₁ Prediction

Sex	Ethnicity	Intercept (b ₀)	Age (b ₁)	Age ² (b ₂)	Ht (cm) ² (b ₃)
Male	Caucasian < 20 yr of age	-0.7453	-0.04106	0.004477	0.00014098
Male	Caucasian ≥ 20 yr of age	0.5536	-0.01303	-0.000172	0.00014098
Male	African-American < 20 yr of age	-0.7048	-0.05711	0.004316	0.00013194
Male	African-American ≥ 20 yr of age	0.3411	-0.02309	0	0.00013194
Male	Mexican-American < 20 yr of age	-0.8218	-0.04248	0.004291	0.00015104
Male	Mexican-American ≥ 20 yr of age	0.6306	-0.02928	0	0.00015104
Female	Caucasian < 18 yr of age	-0.8710	0.06537	0	0.00011496
Female	Caucasian ≥ 18 yr of age	0.4333	-0.00361	-0.000194	0.00011496
Female	African-American < 18 yr of age	-0.9630	0.05799	0	0.00010846
Female	African-American ≥ 18 yr of age	0.3433	-0.01283	-0.000097	0.00010846
Female	Mexican-American < 18 yr of age	-0.9641	0.06490	0	0.00012154
Female	Mexican-American ≥ 18 yr of age	0.4529	-0.01178	-0.000113	0.00012154

L-CsA:

Treatment of BOS after SLT

Protocol Number:

BT – L-CsA – 301 – SLT

Sponsor:

Zambon SpA

The age to be considered is at the time of personal best post-transplant FEV₁ (it has to be derived based on the date of personal best post-transplant FEV₁ versus the date of collection of Demographic information). Since only the year of birth is provided in the CRF, the age at the time of personal best post-transplant FEV₁ will be calculated considering the central day of the year for all patients (02/JUL/YEAR OF BIRTH).

Due to eCRF study design, ethnicity has not been recorded as required for Table 2, and as a result, the race field as recorded in the eCRF will be used for mapping as detailed below in Table 3.

Table 3: eCRF Race Classification

eCRF Term	Remapping
White	Caucasian
Black or African American	African-American
Asian	0.88% reduction will be used versus the Caucasian
Other	
check "other, specify" to see additional race info.
 
 - If patients are defined as "white" or "black/African", please use the corresponding classification. - If patients are defined as "latinos", then use "Mexican-American". - If patient is defined as "Arabian" then treat as the Asian category with the 0.88% reduction used versus the Caucasian. 
Otherwise consider them as "unknown"

For Asian or Other field with Arabian ethnicity, the calculation will be performed using the Caucasian coefficients of Table 2 (considering the corresponding sex, age, and height values) and then applying a correction factor of 0.88 [88]. For example, in case of an Asian male patient older than 20 years, the calculation will be:

$$\text{Predicted FEV}_1 = 0.88 * (0.5536 - 0.01303 * \text{age} - 0.000172 * \text{age}^2 + 0.00014098 * \text{height}^2).$$

In case of other races (American Indian or Alaskan, Native, Native Hawaiian or Other, Pacific Islander), unknown, or unspecified ethnicities (including "multiracial", "multicultural", "mixed", etc.), parameters calculated as average of the Caucasian, African-American, and Mexican-American parameters will be used, according to Table 4:

Table 4: Coefficients for FEV₁ Prediction for other/unspecified ethnicities.

Sex	Age class	Intercept (b ₀)	Age (b ₁)	Age ² (b ₂)	Ht (cm) ² (b ₃)
Male	< 20 yr of age	-0,7573	-0,04688	0,004361333	0,000141
Male	≥ 20 yr of age	0,508433	-0,0218	-0,0000573	0,000141
Female	< 18 yr of age	-0,9327	0,062753	0	0,000115
Female	≥ 18 yr of age	0,409833	-0,00941	-0,000134667	0,000115

12 Immunosuppressants

Immunosuppressants are collected in the Concomitant Medications CRF form.

As per CRF completion guidelines, immunosuppressants are to be collected using the same measurement unit i.e., mg. In those cases where it is not done, considerations will be taken on ongoing basis (at DRM at the latest) to convert units for each immunosuppressive agent to allow cumulative dose to be calculated. Immunosuppressant medications will be coded using the World Health Organization (WHO-DD) classification system and grouped by drug class and PT.

In order to identify immunosuppressants among concomitant medications, any of the following two rules will be applied.

1. Only the following routes are to be considered: oral, intramuscular, intravenous, and subcutaneous; the following codes are to be considered:
 - L04A Immunosuppressants:
 1. L04AA Selective immunosuppressants,
 2. L04AB Tumor necrosis factor alpha (TNF- α) inhibitors,
 3. L04AC Interleukin inhibitors,
 4. L04AD Calcineurin inhibitors,
 5. L04AX Other immunosuppressants;
 - H02AB Glucocorticoids (all);
2. L04AD02 Tacrolimus, and route = sublingual.

CCI

12.1 Basic Immunosuppressants

As per protocol, regardless of treatment assignment, all clinical trial participants must be on a maintenance regimen of immunosuppressive agents including tacrolimus, a second agent such as but not limited to mycophenolate mofetil (MMF) or azathioprine, and a systemic corticosteroid such as prednisone as third agent. At each visit, the average maintenance doses of immunosuppressive agents will be recorded by the Investigator on the Concomitant Medication eCRF.

Basic immunosuppressants refer to maintenance regimen of immunosuppressive agents and include the following:

- Calcineurin inhibitors (Tacrolimus, Cyclosporine A);

- Antimetabolite (Antimetabolite) agents (MMF, Azathioprine);
- mTOR inhibitor (Everolimus, Sirolimus);
- Selective costimulation blocker (Belatacept);
- Corticosteroids.

The total basic immunosuppression administered from the day of randomization will be evaluated.

Basic immunosuppressives will be coded by Anatomical Therapeutic Code (ATC) codes, and will be summarized by treatment group for SAF, FAS and PPS.

A p-value will be obtained from the Fisher's Exact test for the comparison of patients with any basic immunosuppressants from L-CsA plus SoC versus patients with any basic immunosuppressants from SoC alone, for each class of basic immunosuppressants listed above.

Descriptive statistics on cumulative doses for basic immunosuppressants will be provided:

- for the whole treatment period (from day of randomization to end of study)
- for each period between study visits (V1 to V2, V2 to V3, etc.)
- cumulatively for each period between study visits (V1 to V2, V1 to V3, V1 to V4, etc.),

where periods between study visits V_i to V_{i+1} (with $i=2,3,4$, etc) is defined as the interval starting from the first day post visit V_i and ending the last day of visit V_{i+1} (included). For V1 to V2 the date of V1 must be considered too.

Descriptive statistics will be calculated for each class of basic immunosuppressants listed above and overall. If a patient took more than one basic immunosuppressant related to the same class, then the total dose will be taken into consideration in the calculation.

P-values will be obtained from the Fisher's Exact test for the comparison of patients with any basic immunosuppressants, including each of basic immunosuppressant listed above from L-CsA plus SoC versus patients with any basic immunosuppressants from SoC alone at each time interval (V1 to V2, V1 to V3, ,V1 to V9).

Exposure to immunosuppressant medication details will be summarized similarly for each category of basic immunosuppressant, and overall for all.

This includes the calculation of the duration of intake (date of last basic immunosuppressant intake – date of first basic immunosuppressant intake + 1). The duration will be calculated by summing the duration of the associated treatments. The overlapping days will be counted only once.

The ratio between the cumulative dose and intake duration will be used to produce the dose per day. The overall dose per day per patient will then be displayed for each treatment group for each time interval along with the 95% confidence interval.

By-patient listings will be provided for all basic immunosuppressants for FAS.

12.2 Other Immunosuppressants

Other immunosuppressants refer to all the immunosuppressive therapies that are not classified as maintenance regimen as described in section 12.1 (but meet the conditions reported in section 12). Other immunosuppressive therapies will be coded by ATC codes, and will be summarized by treatment group for SAF, FAS and PPS.

All other immunosuppressants administered from the day of randomization will be evaluated. The number (%) of patients taking any other immunosuppressants will be provided overall and for each ATC code.

The same summary statistics for cumulative dose and for exposure as described in section 12.1 will be provided.

13 Prior and concomitant medications

Prior medications are those medications taken prior to randomization with a stop date and time prior to the randomization date/time (standard definition of prior/concomitant medications considers the first dose of study treatment but, as in this study SOC group won't have any first dose date, randomization date will be considered instead).

Concomitant medications are those medications with a start date and time on or after the randomization date/time, or those with a start date and time before the randomization date/time and either a stop date and time on or after the study randomization or are ongoing at the end of the study.

Prior and concomitant medications will be summarized by ATC codes and listed for FAS. Prior/concomitant medications will be coded using the WHO-DD classification system and grouped by drug class and PT.

14 EFFICACY

For each efficacy analysis, the adequacy of the model assumptions will be checked, and if it is found that these are inadequate then alternative approaches may be performed.

For all variables assumed to be normally distributed, the conditional studentized residuals from this model will be tested using the Shapiro-Wilk test. If the assumption of normality of these residuals is violated, then a log-transformed model will be fitted. The need for a possible log transformation of these variables will be investigated prior to unblinding by assessing the model

residuals without a treatment term. Where data are transformed for analysis, back transformation will be applied for the presentation of results. Presentation of the tables will be amended as needed for this, with the addition of an explanatory footnote.

Classification and imputation of missing data will be completed prior to any transformation of the data for analysis.

As a general remark for all efficacy endpoints based on spirometry data, values collected at 1h and 4h post dose will not be used for any efficacy analyses as they are collected only for safety evaluations.

It is important to note that due to the decrease in sample size (see section 8.2) the study will be underpowered for the assumed effect to assess the statistical hypothesis for the primary endpoint. The statistical modelling for the primary endpoint for the pre-specified covariates may lead to non-convergence of the models and selective covariates will have to be considered. Supplementary analyses for the primary endpoint, **CCI** will adopt simple statistical analyses. As a result, all analysis for this study will be descriptive in nature.

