14.1 PRIMARY EFFICACY ANALYSIS

14.1.1 Analysis Population and Estimand

The primary endpoints will be analyzed using a “composite strategy” (International Conference on Harmonization (ICH) guideline E9 addendum on estimands and sensitivity analysis in clinical trials to the guideline on statistical principles for clinical trials). The estimand is defined by the following:

- Population: adult recipients of a single pulmonary allograft with clinically defined BOS, matching the inclusion and exclusion protocol criteria.
- Variable: FEV₁ data at Week 48 (visit 9) collected from the on site **CCI** spirometer (data collected with the **CCI** home spirometer will be used for supplementary analyses). Only accepted over-reader best FEV₁ data for the session from **CCI** will be used for analysis; data will not be re-derived.
- Intercurrent events: After IEs such as stopping treatment with L-CsA, augmentation of SoC therapy, etc., FEV1 measurements will still be collected and used in the analysis. In case of IEs preventing the use of FEV1 measurements, i.e. death and re-transplantation, the FEV1 will be imputed as treatment failure: FEV1 equal to zero for all visits subsequent the event. Rejected spirometries are those that did not meet the American Thoracic Society criteria; if rejected, then they would be re-done but there may be cases where they are rejected twice and resulting in missing data. Rejected spirometry is not an indicator of a better/worse outcome and can be assumed to be MAR.

- Population-level summary: difference in mean change from baseline in the FEV₁ at week 48 between treatment groups.

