14.1.2 Working Hypothesis

The alternative hypothesis (H_1) for this trial is that L-CsA plus SoC is superior to SoC alone in preserving FEV₁, i.e., under H_1 it is expected that patients treated with L-CsA plus SoC will exhibit a smaller mean FEV₁ decline between baseline and the end of Week 48 than those who receive SoC alone.

Due to the decrease in sample size (see section 8.2) then there will be an underpower to assess the statistical hypothesis, and instead the primary analysis will be descriptive in nature.

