14.1.3 Analysis Model

The primary efficacy analysis will be carried out using a LMM for repeated measurements, using all observed available FEV₁ measurements. In case of death or re-transplantation events, FEV₁ will be imputed as zero at each nominal day post event.

The dependent variables are the absolute change from baseline of FEV₁ measurements at visit 2 (i.e., the first post-baseline visit) through visit 9 (Week 48). For the definition of baseline FEV₁ please refer to section 8.1.1.

A flexible and robust model will be chosen for the random part of the LMM according to a pre-specified stepwise procedure (see next section). The original protocol considered the fixed part of the LMM containing the following (except from the intercept): time cubic splines, treatment, the interactions of time splines by treatment, baseline FEV₁, the interactions of time splines with the baseline FEV₁, region (North America versus all other countries together), underlying indication for lung transplant (COPD versus all others), and use of azithromycin at randomization (i.e. Baseline, Visit 1). Due to the reduced sample size (see section 8.2), the covariates will be selected taking into account model convergence (as detailed below).

The primary efficacy parameter will be estimated from the model by the adjusted difference between treatment groups in mean FEV₁ change from baseline after 48 weeks. The p-value for the null hypothesis of no difference and a two-sided 95% confidence interval for the difference will be provided. The comparison between treatment groups at all the other visits (2-8) will also be presented.

A figure of observed mean change from baseline and standard errors at each visit, by treatment group will be presented. A figure with adjusted mean changes from baseline at each visit by treatment group derived from the LMM will be provided.

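### The SAP's log-transform rule does not fit the primary FEV1 model: changes are often negative, and log(FEV1) fails once a death or re-transplantation is scored as zero

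*SAP*

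**What the plan says.** SAP section 14 sets one rule for every efficacy variable assumed to be normal. Conditional studentized residuals are tested with Shapiro-Wilk; "If the assumption of normality of these residuals is violated, then a log-transformed model will be fitted". The need for a log is judged before unblinding, from a model without a treatment term. On order of operations: "Classification and imputation of missing data will be completed prior to any transformation of the data for analysis". On reporting: "Where data are transformed for analysis, back transformation will be applied for the presentation of results". A general clause adds that model assumptions will be checked and "if it is found that these are inadequate then alternative approaches may be performed", without naming any approach.

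SAP 14.1.3 defines the primary outcome: "The dependent variables are the absolute change from baseline of" FEV1 at visits 2 to 9. For death and re-transplantation, SAP 14.1.1 says "the FEV1 will be imputed as treatment failure: FEV1 equal to zero for all visits subsequent the event". The estimand's summary measure is "Population-level summary: difference in mean change from baseline in the" FEV1 at Week 48 between the arms.

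Two other fallbacks exist, neither for the primary model. SAP 14.2.1 gives a rank transformation for the supplementary ANCOVA, reached only if normality still fails after a log. SAP 14.5 gives a Mann-Whitney test for subgroup comparisons. The version history shows that SAP 3.0 introduced both the zero imputation and the ranked ANCOVA. Nothing visible in the log rule provides for zeros.

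**The concern.** The rule is worded as mandatory, and it is the only named response to non-normal residuals in the primary model. Taken literally, it asks for the log of a quantity that is often negative. Read charitably as log(FEV1), it meets log(0) after any death or re-transplantation, because the zeros are filled in before any transformation. Even where log(FEV1) can be fitted, its back-transform is a ratio, not the difference in mean change that the estimand names.

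Protocol section 15 makes the final SAP the analysis of record. If the rule is triggered and cannot be applied, the analyst has to improvise. The obvious improvisation, fitting log(FEV1) to the positive values, drops the failures that the composite strategy was added to count.

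**Working it through.** **Inputs.** Difference 200 mL, SD 350 mL, one-sided alpha 0.025, 50 per arm for at least 80% power, and 62 patients randomized (SAP 8.2). Monthly slopes of -0.008 L and -0.045 L in the earlier investigator-initiated trial (Protocol 7.1.4). The documents give no event count and no baseline FEV1, so both are assumed below.

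**The plan's own figure.** Normal approximation: n = 2 × (1.960 + 0.842)² × 350² / 200² ≈ 48.1, so 49 per arm. Noncentral-t power at 50 per arm is 0.808. The stated figure reproduces, and the 350 mL SD is used below.

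**Reading 1: log of the change.** P(change < 0) = Φ(-mean / 350 mL).

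| Assumed Week-48 means, L-CsA / control | L-CsA negative | Control negative |
|---|---|---|
| 0 / -200 mL | Φ(0) = 50% | Φ(0.571) = 72% |
| -100 / -300 mL | Φ(0.286) = 61% | Φ(0.857) = 80% |
| Earlier-trial slopes × 11.04 months: -88 / -497 mL | Φ(0.252) = 60% | Φ(1.419) = 92% |

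Even if every patient came from a population gaining 200 mL on average, 28% of changes would be negative. The chance that none of 62 is negative would be (1 - 0.284)^62, about 1 in 10⁹. This reading fails in practice.

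**Reading 2: log(FEV1).** It is undefined at every zero-imputed visit. With event time uniform over 337 days, the expected number of such visits per event is (29 + 57 + 85 + 113 + 169 + 225 + 281 + 337) / 337 = 1296 / 337 = 3.85 of 8, always including Week 48. The chance of at least one event among 62 is 1 - (1 - p)^62: 46% at p = 1%, 71% at 2%, 96% at 5%.

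An improvised offset c does not settle it. Take ten patients at 1.5 L, nine ending at 1.3 L and one at zero. The back-transformed mean ratio exp{mean[log(FEV1 + c) - log(baseline + c)]} is 0.42 at c = 0.001 L, 0.67 at 0.1 L and 0.85 at 1 L.

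**Does the zero trigger the rule?** Simulated Week-48 regression of change on baseline, no treatment term, 62 patients, assumed baseline mean 1.5 L and SD 0.4 L, SD of change 0.35 L. Shapiro-Wilk at 5% rejects in about 5% of trials with no event, 46% with one and 70% with two. Across assumed baseline means of 1.0 to 2.0 L and SDs of 0.3 to 0.5 L, the ranges are 14-84% with one event and 21-94% with two. At 1.0 L and SD 0.4 L the rates are only 18% and 27%. A simulation of the full mixed model of SAP 14.1.4 without treatment (200 trials per setting) gave 3%, 80% and 96% with none, one and two events; the last two ranged over 60-92% and 83-99% across assumptions.

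**What would change?** Same Week-48 setting, now with treatment in the model and events random across arms. Removing the zero-imputed patients moves the treatment estimate in volume units by 45 mL on average in absolute size with one event and 53 mL with two (30-61 and 37-68 mL across mean baselines of 1.0 to 2.0 L). The standard error with one event is about 99 mL, and 45 / 99 = 0.45; with two events the shift is again roughly half the standard error. Volume units with zeros kept and log(FEV1) with zeros lost fall on opposite sides of p = 0.05 in 12%, 22% and 27% of trials with none, one and two events. The 12% comes from the change of scale alone; the zeros add 22 - 12 = 10 and 27 - 12 = 15 percentage points.

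**The case against.** Several objections carry weight.

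- A reader might infer that the fallback can never be computed. The documents do not support that. SAP 14.1.1 names the estimand's variable as FEV1 at Week 48, a positive volume, so log(FEV1) is a plausible intention, and with no event it can be fitted. Protocol 15.2.3.1 expects deaths and re-transplantations to be rare; at an assumed 1% risk the chance of none among 62 is 54%. This stands. What remains is that the text never says FEV1 is the logged quantity, and that this reading fails after a single event.
- The primary-analysis code in SAP 17.1 is redacted and could show the logged quantity or an offset. This also stands as a limit. If it does, section 14 should say so too.
- Section 14 permits alternative approaches and makes the log decision before unblinding. That limits choosing on the treatment result. It neither names a substitute nor makes the log computable.
- A reader might infer that a superiority conclusion hangs on the choice. It does not: SAP 14.1.2 says "instead the primary analysis will be descriptive in nature". The p < 0.05 disagreement is therefore only a gauge of how far the outputs differ, and about half of it with one event is present with none.
- The 45 to 55 mL shift compares two volume-unit models, so it measures the loss of the failures rather than the log model itself. It also rests on a single-visit regression. Both are fair limits.

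**Conclusion.** The rule is wrong as written for the primary model. On the literal reading it asks for logs of negative numbers. On the charitable reading it works only if no patient dies or is re-transplanted, and it then reports a ratio where the estimand is a difference. No other visible text supplies a usable named fallback for this model.

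The practical size is moderate. One zero-scored patient can raise the chance of triggering the rule from about 5% to about 46%, though the rise is modest if mean baseline FEV1 is near 1.0 L. Losing the zeros moves the volume estimate by roughly half a standard error. These sizes depend on assumed baseline FEV1, event counts and event timing. The algebraic conflict does not. What is exposed is the estimate, 95% confidence interval and p-value that SAP 14.1.3 still reports. The material does not show the trial to be invalid or its descriptive conclusion to be overturned. The point should be fixed before analysis because the repair is small.

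**What to change.** For FEV1 change:

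1. In SAP section 14, delete the log step.
2. In SAP 14.2.1, delete the condition that makes the rank step follow a failed log.
3. State that the volume-unit mixed model remains the primary estimate whatever the Shapiro-Wilk result. This keeps the estimand as defined and keeps the zeros.
4. If normality fails, report the rank ANCOVA already planned in 14.2.1 beside it as supportive, with the number of deaths and re-transplantations per arm.

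The cost is a short SAP edit, with no new method and no new data. There are two downsides. The rank result has no mL unit. It also uses change to Week 48 only, so it omits survivors without a Week-48 value, whom the mixed model keeps under missing at random. For both reasons it supports the mixed model and does not replace it.
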